#### **STUDY FLOW CHART**

Suitable patients identified and consented from Glaucoma clinics at HH and PCH-visual fields test completed One week prior to the first phasing visit the patient will be asked to start completing their drop compliance diary, continued for the duration of the study IOP phasing for POAG/OHT patients on topical therapy WITHOUT heat (no mask) - first visit IOP phasing for POAG/OHT patients on topical therapy WITH heat - second visit IOP phasing for POAG/OHT patients on topical therapy WITHOUT heat (wearing mask) third visit One to two weeks after completing the study a further visual fields test will be completed safety visit including a visual fields test and visual acuity measure Patient continues with their normal Glaucoma care

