
One to two weeks after completion of the study the patients will undergo a further visual

fields test (Humphrey sita fast 24-2) to ensure no significant progression of their disease has occurred as a result of the study regime. All data will be recorded and stored for analysis at the end of the trial and made available to the standard of care treating clinician. At the end of the trial the patients will continue their Glaucoma visit schedule as requested by their treating Ophthalmologist.

All attempts will be made to have participants complete the study by organising visits that fit in with their timetable and offering further appointments should the participant not be able to attend on a certain day. Participants will be offered reimbursement for travel and refreshments on the day of their study visits. In the case of participant 'drop-outs', the research team will attempt to recruit further participants otherwise patients on whom all the tests could not be performed will be excluded from analysis.

When designing this trial, it was important for us to ensure that the comments and suggestions of the public and patients were taken on board, so that we could confirm that this trial was suitable for people with POAG or OHT. To do this, a patient and public involvement (PPI) forum was be organised on 30th May 2023 and the trial subsequently developed with the help of people diagnosed with Glaucoma in the Cambridgeshire area who agreed that the tests and procedures included in this study were practical and acceptable to patients.

It is the intention of the research team that the results of the study will be disseminated in peer-reviewed articles and at ophthalmic conferences.

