## Secondary analysis:

1. Adverse Events will be analysed using Chi-squared test or a summary by presenting full listing and frequencies & percentages.

2. Quality of Life (QoL) questionnaires will be analysed using normality tests, descriptive statistics and reliability tests.

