## 5.2.2 Datasets

To determine whether there is a significant change in IOP in each participant, the IOP measured with and without the addition of heat over the five time points will be used in a one-way repeat measure ANOVA test will be completed for each day of phasing. A paired ttest will be used to establish significance between an individual's IOP measure at a certain time point with or without the addition of heat. A difference of 1.5mmHg in IOP mean deviation would be considered a significant change of IOP. This value has been used in previous Glaucoma studies (Allergan Bimatoprost SR and Thea In-Sight) to provide a 95% confidence interval. A paired t-test will be used to establish any significant change in BCVA at baseline and exit visit based on a mean SD change of 0.1 logMAR or 5 ETDRS letters. Ocular safety parameters, QoL (EQ-5D-5L) and OSDI questionnaires, visual fields and slit-lamp exam measures will be summarised for the cohort by mean, standard deviation (SD), median, minimum and maximum values. A non-parametric analysis (Wilcoxon signed rank test) will be used if the data is found to not be normally distributed. Ocular adverse events and safety variables will be tabulated by whether the participant has received heat treatment or not before instilling their anti-hypotensive eye drops. Normality of the data will be checked by plotting histograms of the data (separately before and after the heat) and not using stats tests. Differences will be considered statistically significant P values less than 0.05.

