## 7.1.2 Exclusion criteria

Patient will NOT be eligible if ONE or MORE of the following criteria is met:

- > Fundus examination not performed or not available within 12 months
- > Visual field not performed or not available within 12 months
- > Advance stage of Glaucoma, defined by at least one of the following criteria:
- > Absolute defect in the ten degrees central point of the visual fields
- ➤ Severe visual field loss: MD < -18 dB

> Risk of visual field worsening as a consequence of participation in the study according

- to the investigator's best judgment
- Far best corrected visual acuity ≥ +0.7 logMAR

 $\succ$  History of trauma, infection, clinically significant inflammation within the previous three months

- Ongoing or known history of ocular allergy and/or uveitis and/or viral infection Clinically significant or progressive retinal disease (e.g. retinal degeneration, diabetic retinopathy, retinal detachment)
- > Presence of at least one severe objective sign among the following:
  - Conjunctival hyperaemia (Grade 5 Efron scale)
  - Superficial punctate keratitis (Grade 4/5 Oxford scale)
  - Blepharitis (Grade 3 Efron scale)
  - > Severe dry eye as assessed by the investigator
  - ➤ Corneal ulceration
  - > Any palpebral abnormality incompatible with a good examination

> Any other abnormality preventing accurate assessment e.g. reliable tonometry measurement, visual field examination, fundus examination.

 $\succ$  A patient judged to have poor compliance with their glaucoma drops according to the investigator's best judgement

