#### 11. APPENDICIES

## 11.1 Appendix 2 – Schedule of Procedures

Procedures	Visits					
	Identification and consent	Visit 1- phasing without heat	Visit 2- phasing with heat	Visit 3-phasing with mask but no heat	Visit 4 – safety check	
Informed consent	x					
Demographics	x					
Medical and ocular history	х					
QoL questionnaires		x	x	X		
OSDI questionnaire		x	x	x		
Visual fields	x				x	
Drop compliance diary	x	x	x	X		
Slit-lamp examination		x	x	X		
Corneal fluorescein stain (Oxford grading)		x	x	х		
Meibomian gland dysfunction (Efron grading)		x	x	x		

HALO – PROTOCOL

			Nort	<del>h West Anglia</del>		1
Conjunctival hyperaemia (Efron grading)		х	x	HS Foundation Trust		
Application of Blephasteam®			x			
Instillation of habitual hypotensive eye drops		Х	x	x		
IOP @ 08:30 +/- 30 mins		х	x	x		
IOP @ 10:30 +/- 30 mins		х	x	x		
IOP @ 12:30 +/- 30 mins		х	x	x		
IOP @ 14:30 +/- 30 mins		х	x	x		
IOP @ 16:30 +/- 30 mins		х	x	x		
Adverse events		Х	x	х		
Far best corrected visual acuity (BCVA)		х	x	x	х	
Verification of inclusion and exclusion status	x					

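### The exit visual field is meant to rule out progression in the participants, but the planned cohort summary commits to no within-participant change and no count or listing of those who worsened

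*Protocol*

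**What the plan says.** Section 5 schedules a further field test (Humphrey 24-2) after the three phasing visits, "to ensure no significant progression of their disease has occurred as a result of the study regime". The Study Flow Chart agrees on timing: "One to two weeks after completing the study a further visual fields test will be completed". The Schedule of Procedures marks visual fields twice only, at identification and consent and at visit 4.

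For analysis, section 5.2.2 says that "visual fields and slit-lamp exam measures will be summarised for the cohort by mean, standard deviation (SD), median, minimum and maximum values". It does not say whether the quantity summarised is the field level or its change.

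Three other provisions are relevant:

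- Visual acuity, in the same section: "A paired t-test will be used to establish any significant change in BCVA at baseline and exit visit", with a size of change named (0.1 logMAR or 5 ETDRS letters).
- Safety variables, also in 5.2.2: "Ocular adverse events and safety variables will be tabulated by whether the participant has received heat treatment or not".
- Adverse events, under Secondary analysis: a chi-squared test or "a summary by presenting full listing and frequencies & percentages".

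Section 5 also restricts statistical analysis to the right eye, although the mask treats both eyes.

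**The concern.** The stated purpose and the stated method answer different questions. Whether disease progressed under the study regime is settled by comparing each participant's exit field with that person's own earlier field. A mean, SD, median, minimum and maximum for the cohort describe a group. In a mixed POAG and OHT sample, with mean deviation (MD) allowed down to -18 dB, the spread between people can swamp a substantial loss in one or two of them.

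Followed literally, the trial could print two similar columns of summary statistics and report that fields were unaffected while one or two participants had lost field. The title promises both efficacy and safety, and sections 2 and 4.2 present the results as the basis for a larger study, so such a statement would be carried forward.

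**Working it through.** The plan gives no figure for the visual-field analysis to reproduce. The sample of 24 rests on pilot-study references and budget (section 7.2.1).

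**Step 1: can another provision supply the individual comparison?**

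- *Tabulation by heat or no heat.* One field precedes all phasing visits and the other follows all of them. Neither belongs to a heated or an unheated day, so the split cannot be applied.
- *Adverse-event listing.* Field worsening is not defined as an adverse event, and the Schedule of Procedures marks adverse events at visits 1 to 3 only, not at visit 4, when the exit field is done.
- *Visual acuity.* The paired comparison is written for acuity alone.

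None of them fills the gap.

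**Step 2: effect on the mean (arithmetic).** If k of 24 participants each lose L dB of MD, the mean shifts by k × L / 24. The values of L are illustrations, not proposed criteria.

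| L | k = 1 | k = 2 |
|---|---|---|
| 6 dB | 6/24 = 0.25 dB | 12/24 = 0.50 dB |
| 10 dB | 10/24 = 0.42 dB | 20/24 = 0.83 dB |

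**Step 3: effect on the SD and minimum of levels (simulation).** The following assumptions are not in the protocol. Baseline MD is normal with mean -4 and SD 4, or mean -7 and SD 5, both truncated to -18 to +2 dB; or uniform from -18 to 0 dB. Random error with SD 1 dB is added to the second field. Each setting has 40,000 cohorts of 24.

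- The between-participant SD after truncation is about 3.5, 4.3 and 5.2 dB, many times the shift that one 6 dB loss makes in the mean.
- In the first setting the exit SD is 3.61 dB with retest error alone. It is 3.80 dB with one 6 dB loss (a rise of 0.19) and 3.98 dB with two (a rise of 0.37).
- The share of cohorts in which the minimum falls by at least 3 dB, across the three settings, is:

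| Loss | One participant | Two participants |
|---|---|---|
| 6 dB | 15–22% | 27–37% |
| 10 dB | 40–46% | 63–69% |

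**Step 4: the same data as within-participant change.** The largest listed loss is no more than 2 dB short of the true loss in about 98% of cohorts with one affected participant, and in more than 99% with two.

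**Step 5: is mean change enough?** No. A two-sided 5% paired t-test on the change is significant in about 1–3% of cohorts with one affected participant and 3–7% with two. One or two large changes inflate the SD of the differences as well as the mean.

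**Step 6: what a clean result could claim.** With 0 of 24 worsened, the one-sided 95% upper limit is 1 − 0.05^(1/24) = 11.7%. The upper end of the two-sided 95% exact interval is 1 − 0.025^(1/24) = 14.2%.

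**The case against.** The strongest reply is that the sentence in 5.2.2 is ordinary descriptive wording, and that the derivation of change, flags and listings is normally left to a statistical analysis plan. The text does not say levels. If changes were summarised, the reported minimum would be the worst individual loss and most of the problem would go. The signed-rank test named as the fallback in that section is a paired method, so this reading is open. This stands in part: levels is an inference, and the protocol should say which is meant. But the protocol does fix a method for fields, and it fixes a paired one for acuity and not for fields. Even on the favourable reading, nobody is counted.

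A reader might go further and infer that a loss in one or two participants could not show at all. The simulation does not support that. The minimum is reported, and it sometimes moves, more often for a 10 dB loss or in an eye that was already poor.

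A reader might also infer that the protocol expects field harm in those enrolled, because section 7.1.2 speaks of "Risk of visual field worsening as a consequence of participation in the study according" to the investigator's judgement. That line is an exclusion criterion: it keeps such patients out. Section 8.1 calls the risk of wearing the masks negligible.

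Lastly, section 5 makes the data available to the treating clinician, so participants are not left without individual review. That is true, but it is individual care and produces no trial result.

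**Conclusion.** The point holds as a mismatch between purpose and method. The exit field is there to check for progression in the participants. The stated summary commits to no within-participant change and to no count or listing of worsened participants, and no other provision supplies them.

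Read as levels, the summary would usually, but not always, miss a 6 dB loss in one or two of 24. The shifts in the mean are arithmetic. The percentages for the minimum depend on the assumed MD distributions and retest error. The documents do not suggest that losses of this size are likely; heat is applied at one visit only, for ten minutes.

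The word ensure also claims too much. Sections 5 and 7.3 accept a baseline field up to three months old, so part of any change may predate the study. One pair of fields in 24 people, even with no worsening seen, leaves a rate of up to 11.7% compatible with the data.

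This is a worthwhile and cheap improvement to a safety analysis. It does not bear on the primary IOP comparison.

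**What to change.** In section 5.2.2, take visual fields out of the general summary sentence and state instead:

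- Fields are analysed as within-participant change, visit 4 minus the pre-study field.
- Every participant's change is listed for both eyes. Both eyes are heated, so the right-eye-only rule in section 5 should not limit this safety listing.
- The number of participants meeting a progression criterion is reported with an exact confidence interval, counting by participant so that the denominator stays at 24. The investigators choose the criterion and fix it before the data are seen.
- Mean change with a 95% interval may be added, but it is not sufficient alone.

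In section 5, describe the exit field as a check for short-term change.

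The cost is wording only, since both fields are already scheduled. The small downside is that test-retest noise will flag some eyes falsely, so each flagged eye needs a comment beside the listing.

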The patient will attend the clinic for three separate visits each approximately one week apart. starting with phasing 'without heat', then phasing 'with heat' and lastly phasing wearing the Blephasteam mask but with no heat as a control. The Blephasteam mask will only be used on the days of the clinic visits, the participants will not be required to use the device at home. The water carrier inserts for the masks will be designated to the same patient throughout the study for hygiene reasons. The inserts for the mask will be moistened and fitted according to the manufacturers' instructions. The wireless device will be left to reach temperature for 3-4 minutes then the patient will be asked to wear the mask and be instructed to keep their eyes closed, this occurs once at the start of each visit. The device warms the ocular surface for a set time of 10 minutes, after which the participants will remove the mask and instil their habitual Glaucoma eyedrops. They will be instructed to close their eyes and apply light pressure on the inner corner of the eye for 30 seconds. The IOP will then be measured at the first time point with the ORA and Goldman devices. Although both eyes will be treated with the heat mask only the right eve results (to eliminate bias) will be used for the statistical analysis. During the visits the patients' will have their best corrected visual acuity (BCVA) reviewed before and after measurements are taken. IOPs are measured first using the ORA tonometer (Reichert Inc., Germany) followed by the Goldman tonometer (Haag-Streit AG, Switzerland) five minutes later as per previous studies measuring IOP with the sequential use of tonometers (Tejwani et al., 2015). These IOP measures are taken at five set time points during the day called 'phasing': 08:30 +/- 30 mins, 10:30 +/- 30 mins, 12:30 +/- 30 mins, 14:30 +/- 30 mins and 16:30 +/- 30 mins. An average of three measures will be taken using the ORA machine, when using the Goldman tonometer three measures will only be taken if the first two are not within >2mmHg of each other. The procedure for the Goldman tonometer will be as follows: Two individuals (an operator and a reader) will perform the readings for the study visits. The operator will be responsible for operating the slit lamp, tonometer, and the instrument dial, while the reader will read and record the results. A full anterior segment slitlamp examination will be performed at the end of each phasing visit to ensure there are no adverse effects experienced following the treatment, including grading of the Meibomian glands (Efron scale). Additional assessments include adverse events and quality of life and ocular questionnaires.

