## **5.2 Statistical Methods**

## 5.2.1 General:

Data will be presented using descriptive statistics; continuous data will be summarised using means & standard deviations if normally distributed otherwise using median and interquartile

Version 1.0 13/JUN/2023

range. For categorical data frequencies and percentages will be reported. Missing data will be reported.

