## 8.1 Assessment and management of risk

In terms of benefits to participants, the heat masks may result in a significant and meaningful effect by reducing the IOP in combination with their ocular hypotensive eye drops. A secondary effect may be to improve any existing MGD for which the device is usually indicated. Heat therapy is the standard treatment regime for obstructive meibomian gland dysfunction (MGD). This would increase the quality of the tear film, by enhancing the meibum supply from the glands situated on the upper and lower eye lids. If clinical effectiveness is shown, the Blephasteam® would provide a non-invasive treatment option for one of the most common causes of reversible blindness (Blomdahl et al., 1997). This would also reduce the chance that patients would need to progress to dual eye drop therapy or surgical intervention.

The risks of wearing the masks are negligible; a recent study stated that the Blephasteam® device provided safe and effective warmth to the ocular area without any adverse effects on the ocular surface in this study (Purslow et al., 2010; Villani et al., 2012). Each patient will receive their own insert for the Blephasteam® device to use throughout the study to ensure there will be no cross contamination between patients.

Compliance with the heat-masks may be an issue but all site personnel will stress optimal compliance with all patients and ensure that instructions are followed by helping the patient use the device at the time of the visit.

Blephasteam ® CE certified medical device.

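### Ordinal slit-lamp grades are to be summarised by cohort mean, SD, median and range, which can hide worsening within participants

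*Protocol*

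**What the plan says.** Section 5.2.2 lists the summaries for the secondary measures and includes the slit-lamp examination among them: "slit-lamp exam measures will be summarised for the cohort by mean, standard deviation (SD), median, minimum and maximum values".

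The schedule of procedures (Appendix 2) shows three graded signs at visits 1, 2 and 3: "Corneal fluorescein stain (Oxford grading", "Meibomian gland dysfunction (Efron grading" and "Conjunctival hyperaemia (Efron grading", the parentheses closing after each scale name.

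Three other places bear on how these grades should be handled:

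- Section 5.2.1 sets the general rule: "For categorical data frequencies and percentages will be reported".
- Section 5 gives the purpose of the examination that closes every phasing day: "to ensure there are no adverse effects experienced following the treatment, including grading of the Meibomian glands (Efron scale".
- Section 8.1 raises the prospect of benefit on one of the scales: "A secondary effect may be to improve any existing MGD for which the device is usually indicated".

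Section 5.2.2 also tabulates ocular adverse events and safety variables by whether heat was given, and allows a Wilcoxon signed rank test for non-normal data. Section 5.2.1 (secondary analysis) allows a full listing of adverse events. No within-participant change in the slit-lamp grades is specified.

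**The concern.** Oxford and Efron grades are ordered categories. The general rule in section 5.2.1 suits them, yet the specific sentence in section 5.2.2 treats them like continuous measurements. An SAP author would normally follow the specific sentence.

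The larger problem is the mismatch with purpose. Whether an adverse effect followed treatment is asked of each participant, comparing the heat visit with a visit without heat. The five planned statistics describe the spread of grades at one visit and cannot show who moved or in which direction. Section 3 also wants MGD status recorded so that the contribution of MGD improvement to the outcome can be judged, and that too needs change within participants.

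The study title names safety, and section 2 presents the study as the basis for a larger one. A flat mean grade could be carried forward as reassurance about the ocular surface when the summary cannot support that.

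**Working it through.** The protocol states no figure for the slit-lamp grades, so there is nothing to reproduce. The check asks whether the five planned statistics can stay still, or nearly so, while participants worsen.

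**Inputs.** n = 24 (section 7.2.1). Scales and visits are from Appendix 2. One grade per participant per visit is assumed. All grade patterns below are assumed.

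**1. Equal offset (relevant to MGD, where improvement may occur).** Without heat, let grades 0, 1 and 2 have 4, 10 and 10 participants. With heat, 6 go from 1 to 2 and 6 go from 2 to 1, so the counts are again 4, 10 and 10.

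- Mean = (4×0 + 10×1 + 10×2)/24 = 30/24 = 1.25 at both visits.
- Sum of squares about the mean = (10×1 + 10×4) − 24×1.25² = 50 − 37.5 = 12.5, so SD = √(12.5/23) = 0.74 at both visits.
- Median 1, minimum 0 and maximum 2 at both visits.
- Participants who worsened: 6/24 = 25.0% (exact 95% CI 9.8% to 46.7%).

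**2. Unequal offset (MGD).** Without heat, 8 participants are at each of grades 0, 1 and 2. With heat, 4 go from 0 to 2, 4 from 2 to 1 and 4 from 1 to 0, which again gives 8, 8 and 8.

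- Net change = 4×2 − 8×1 = 0.
- Mean 1.00, SD √(16/23) = 0.83, median 1, minimum 0 and maximum 2 at both visits.
- Worsened by two grades: 4/24 = 16.7% (exact 95% CI 4.7% to 37.4%).

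**3. Dilution without improvers (relevant to staining and hyperaemia).** If 5 of 24 worsen by one grade and nobody improves, the mean rises by 5/24 = 0.21 whatever the starting pattern. Take starting counts of 10, 8 and 6 at grades 0, 1 and 2, and let the five move from 0 to 1, giving 5, 13 and 6.

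- Mean: 20/24 = 0.83 becomes 25/24 = 1.04.
- SD: √(15.33/23) = 0.82 becomes √(10.96/23) = 0.69.
- The 12th and 13th ordered values are 1 before and after, so the median stays 1. Minimum stays 0 and maximum stays 2.

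The worsening is still in the mean, but small, and the median and range show nothing.

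**4. What the maximum would catch.** Section 7.1.2 excludes severe staining, "Superficial punctate keratitis (Grade 4/5 Oxford scale" (parenthesis closing there), and grade 5 hyperaemia. If nobody has such a grade at visit 1, a participant who newly reaches it at visit 2 raises the reported maximum. So for these two scales it is mild change that can stay hidden. Section 7.1.2 lists no excluded grade for MGD as such, so the maximum gives less protection there.

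**The case against.** A reader might infer that worsening on every scale will be cancelled by an improvement the protocol expects. The documents do not support that. Improvement is mentioned only for MGD and the tear film quality that depends on it, and only as something that may happen. Heat is applied at a single visit, so same-day MGD improvement large enough to mask harm is itself an assumption. For staining and hyperaemia no improvement is anticipated, and the problem there is dilution. Nor should it be inferred that severe harm would go unseen: new severe staining or hyperaemia would normally raise the maximum.

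Other safeguards exist. Adverse events are collected at visits 1 to 3 and may be listed in full, so a harmful change has a participant-level route into the report. That helps only where a grade change is recorded as an event, and the protocol gives no rule for this. Tabulation by heat or no heat compares two sets of cohort summaries, and the signed rank test addresses net change; neither shows how many worsened.

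Sections 5.2.1 and 5.2.2 could be read as cumulative, with counts reported as well as means. The text does not exclude this but does not say it either. Table layout is often left to an SAP. Here, though, the protocol itself names the statistics, so the choice is already made.

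Finally, a 6-against-6 swap of one grade is also what random grading variation could produce, so 25% worsened need not mean harm from heat. That stands, and it is why the comparison of the two no-heat visits belongs in the fix.

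**Conclusion.** The point holds in a limited form. Section 5.2.2 commits ordered grades to cohort statistics that sit awkwardly with section 5.2.1 and cannot show the within-participant worsening that the examination is meant to detect. For MGD, all five statistics can be unchanged while about 17% to 25% of participants worsen in the constructed examples. For staining and hyperaemia, mild worsening in 5 of 24 shifts the mean by 0.21 grade.

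These sizes rest on assumed grade patterns with n = 24. They show what the summaries can conceal, not what will happen. The matter is one of descriptive safety reporting and does not touch the primary IOP analysis. The change is worth making because it is nearly free.

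**What to change.** In section 5.2.2, state that the section 5.2.1 rule for categorical data governs the Oxford and Efron grades, and keep mean and SD for continuous measures. For each scale report:

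- the number and percentage of participants at each grade, by visit;
- a within-participant cross-table of visit 2 (heat) against visit 1 and against visit 3 (mask without heat);
- the number and percentage who worsen by at least one grade at visit 2, for each comparison;
- visit 3 against visit 1 in the same layout, so that grading variation without heat on the day can be seen. Because visit 3 always follows the heat visit by about a week, any lasting effect of heat would also appear there;
- for staining and hyperaemia only, the number newly reaching a grade that section 7.1.2 already lists as severe.

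The cost is a short edit to the protocol or SAP and a few extra tables. All grades are already collected at visits 1 to 3, so no examination, visit or participant is added.
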